## 5.3. Handling and Storage of Study Treatment

Dabrafenib and trametinib must be dispensed and administered in accordance with the protocol, and only to subjects enrolled in the study. Dabrafenib and trametinib must be stored in a secure area under the appropriate physical conditions for the product. Study medication is to be stored at the temperature specified on the label. Maintenance of a temperature log (manual or automated) is required. Access to and administration of dabrafenib and trametinib will be limited to the investigator and authorized site staff.

Procedures for final disposition of unused study treatments will be provided in the Study Procedures Manual (SPM).

## 5.4. Treatment Assignment

Subjects will be entered into the appropriate cohort based on the mutation and disease status. Subjects will be identified by a unique subject number that will remain consistent for the duration of the study. Each site will be given a subject number range. This can be obtained from your site monitor.

Upon obtaining consent from the subject for the study the subject will be registered into interactive voice response system (IVRS), by the investigator or authorized site staff to register and record subject activity. Study-specific instructional worksheets will be provided for the use of IVRS.

Once the target number of each cohort has been enrolled, that cohort will be closed to further enrolment and IVRS will no longer allow a subject to be entered.

### 5.5. Blinding

This is an open-labeled study.

### 5.6. Product Accountability

In accordance with local regulatory requirements, the investigator, designated site staff, or head of the medical institution (where applicable) must document the amount of investigational product dispensed and/or administered to study subjects, the amount returned by study subjects, and the amount received from and returned to Novartis, when applicable. Product accountability records must be maintained throughout the course of the study. Refer to the SPM for further detailed instructions on product accountability.

### 5.7. Treatment Compliance

Subjects will be instructed to return treatment bottles at each visit. Compliance with study treatment will be assessed by querying the subject and through pill count at each visit. Compliance will be documented in the source documents and the eCRF.

A record of the number of dabrafenib capsules and trametinib tablets dispensed to and taken by each subject must be maintained and reconciled with study treatment and compliance records. Treatment start and stop dates, including dates of dose modifications and/or interruptions will also be recorded in the eCRF. The investigator will make every effort to bring non-compliant subjects into compliance.

### 5.8. Dose Modification Guidelines

The severity of AEs will be graded using the CTCAE, version 4.0 [www.eortc.be/services/doc/ctc/CTCAE\\_4.03\\_2010-06-14\\_QuickReference\\_5x7.pdf](http://www.eortc.be/services/doc/ctc/CTCAE_4.03_2010-06-14_QuickReference_5x7.pdf). The section includes:

- General guidelines for clinically significant toxicities related to study treatments and
- Specific guidelines for adverse events of special interest, which are events that have been observed with higher frequency or severity in subjects receiving dabrafenib, trametinib, or a combination of both therapies.

**With the exceptions of pyrexia and new primary RAS-mutation positive non- cutaneous malignancies(likely related to dabrafenib); and decreased LVEF, RVO (retinal vein occlusion), RPED, and pneumonitis (likely related to trametinib), the guidance suggests that both therapies be reduced, interrupted or discontinued simultaneously in response to toxicities that are considered by the investigator to be treatment related.**

**Table 3 Categories of Dose Modification Guidelines**

Adverse Event	Dabrafenib	Trametinib	Section
---------------	------------	------------	---------

General Guidelines for Clinically Significant	X	X	5.8.2
Guidelines for Specific Adverse Events			
Cardiovascular Adverse Eventsa			
LVEF		X	5.8.3.1
Hypertension	X	X	5.8.3.2
Prolonged QTc	X	X	5.8.3.3
Skin -Related Adverse Events (Except cuSCC)b or new primary melanomas			
Rash	X	X	5.8.4.1
Hand-Foot Skin Reaction	X	X	5.8.4.2
cuSCC	X	X	5.8.4.3
Other Adverse Events			
Pyrexia	X		5.8.5.1
Diarrhea	X	X	5.8.5.2
Renal Insufficiency	X	X	5.8.5.3
Visual Changes		X	5.8.5.4
Pneumonitis		X	5.8.5.5
Liver Chemistry Stopping Criteria	X	X	5.9.1

- a. For subjects enrolled in France please see [Appendix 9](#) and [Appendix 11](#) for additional dose modification guidelines
- b. Refer to Section [5.8.4.3](#) for management of cuSCC

### 5.8.1. Dose Levels of dabrafenib and trametinib

The dose levels for this study are provided in [Table 4](#).

**Table 4 Dose Level Reduction Guidelines**

Dose Level	Dabrafenib Dose/Schedule	Trametinib Dose/Schedule
Starting Dose	150 mg BID	2 mg once daily
-1 (1 st Dose reduction)	100 mg BID	1.5 mg once daily
-2 (2 nd Dose reduction)	75 mg BID	1.0 mg once daily

Abbreviation: BID = twice daily

If an AE resolves to grade 1 or baseline at the reduced dose level, and no additional toxicities are seen after 4 weeks of study treatment at the reduced dose, the dose may be increased to the previous dose level.

If the subject requires both a dose reduction below 75 mg BID for dabrafenib and a dose reduction below 1 mg once daily for trametinib, the subject must discontinue the combination study treatment.

If a dose reduction below 75 mg BID for dabrafenib is required, dabrafenib will be permanently discontinued but these subjects will be allowed to continue trametinib. If a dose reduction below 1.0 mg once daily for trametinib is required, then trametinib will be permanently discontinued, but these subjects will be allowed to continue dabrafenib.

**Note: Approval from the Novartis Global Clinical Lead is required to restart study treatment after  $\geq 21$  days of interruption.**

### **5.8.2. General Guidelines for Clinically Significant Toxicities on the dabrafenib and trametinib combination treatment arm**

General guidelines regarding management and dose reduction for adverse events that are considered by the investigator to be related to study treatment and which do not have study specific dose modification guidelines as in [Table 3](#) are provided in [Table 5](#) below. These guidelines are intended primarily for toxicities not easily managed with routine supportive care. For example, alopecia is not an indication for dose modification, nor is grade 2 nausea and vomiting that can be easily managed with anti-emetics.

These are general guidelines and investigators should always use clinical judgment in determining dose adjustments for any individual patient. Some toxicities may require hospitalization for stabilization, additional work-up, and consultation with a specialist before treatment can be restarted. Specific adverse events and recommended management include:

- **Pancreatitis** – In the event of abdominal pain or suspected pancreatitis, amylase and lipase laboratory samples should be collected for confirmation of the diagnosis. Patients should be closely monitored when re-starting dabrafenib after an episode of pancreatitis.
- **Uveitis:** Treatment with dabrafenib has been associated with the development of uveitis, including iritis. Monitor patients for visual signs and symptoms (such as, change in vision, photophobia and eye pain) during therapy.
- **Hyperglycemia:** Hyperglycemia requiring an increase in the dose of, or initiation of insulin or oral therapy can occur with dabrafenib. Monitor serum glucose levels as clinically appropriate during treatment with dabrafenib in subjects with pre-existing diabetes or hyperglycemia. Advise patients to report symptoms of severe hyperglycemia such as excessive thirst or any increase in the volume or frequency of urination.

**Table 5 Dose Modification Guidelines for Events Considered Related to Study Treatment (Dabrafenib and Trametinib Combination Treatment)**

CTCAE Grade	Action and Dose Modification a,b
Grade 1 or Grade 2 tolerable	Continue study treatment at same dose level (no dose modification) and monitor as clinically indicated.
Grade 2 (Intolerable) or Grade 3	
1 st , 2 nd	Interrupt study treatment until toxicity resolves to ≤ grade 1 then restart at next lower dose level
3 rd	Discontinue treatment.
Grade 4	
1 st occurrence	Interrupt study treatment until toxicity resolves to ≤ grade 1 or baseline then restart at next lower dose level or discontinue at discretion of investigator
2 nd occurrence	Interrupt study treatment until toxicity resolves to ≤ grade 1 or baseline then restart at two dose levels lower than the starting dose or discontinue at discretion of investigator and after discussion with the GLocal Clinical Lead.
3 rd occurrence	Discontinue treatment

a. Treatment should be discontinued if more than 2 dose reductions are required

b. Approval from the Novartis Global Clinical Lead is required to restart study treatment after ≥21 days

When an individual's adverse reactions are under effective management, dose re-escalation following the same dosing steps as de-escalation may be considered. The dabrafenib dose should not exceed 150 mg twice daily and the trametinib should not exceed 2 mg once daily.

### 5.8.3. Guidelines for Cardiovascular Adverse Events on the dabrafenib and trametinib combination treatment arm

Cardiovascular adverse events have been seen in subjects receiving either dabrafenib, trametinib or both in combination (see the trametinib, dabrafenib and combination IBs for additional information); [GlaxoSmithKline Document Number [HM2009/00151/02](#) 2011; GlaxoSmithKline Document Number [CM2010/00010/02](#) 2011 and GlaxoSmithKline Document Number [2011N126811\\_00](#).2012]

#### 5.8.3.1. Left Ventricular Ejection Fraction (LVEF)

Decreases of the left-ventricular-ejection-fraction (LVEF) have been observed in subjects receiving trametinib monotherapy and in combination with dabrafenib. Therefore, ECHOs must be performed to assess cardiac ejection fraction in regular intervals as outlined in the Time and Events ([Table 19](#)). All ECHOs will be collected; instructions are provided in AgMedNet Imaging Acquisition Guidelines. Dose modification guidance and stopping criteria for LVEF decrease are provided in [Table 6](#)

**Table 6 Dose Modification Guidelines and Stopping Criteria for LVEF Decrease**  
Dose Modification Guidelines and Stopping Criteria for LVEF.

Clinic	LVEF-drop (%) or CTCAE grade	Action and Dose Modification
Asymptomatic	Absolute decrease of >10% in LVEF compared to baseline and ejection fraction below the institution's LLN	
 
• Interrupt trametinib and repeat ECHO within 2 weeksa,b
 
• If the LVEF recovers within 4 weeks (defined as LVEF <math>\geq</math>LLN and absolute decrease <math>\leq</math>10% compared to baseline) 
 
○ Consult with the Novartis Global Clinical Lead and request approval for restart.
 
○ If approved, restart treatment with trametinib reduced by one dose level.
 
○ Repeat ECHO at 2, 4, 8 and 12 weeks after re-start; continue in intervals of 12 weeks thereafter.
 
 
 
• If LVEF does not recover within 4 weeks 
 
○ Consult with cardiologist.
 
○ Permanently discontinue trametinib.
 
○ Report as SAE.
 
○ Repeat ECHO after 2, 4, 8, 12, and 16 weeks or until resolution.
 
 
 

Symptomatic b,c	Grade 3: resting LVEF 39-20% or >20% absolute reduction from baseline Grade 4: resting LVEF <20%	
 
• Permanently discontinue trametinib.
 
• Interrupt dabrafenib.d
 
• Report as SAE.
 
• Consult with cardiologist
 
• Repeat ECHO after 2, 4, 8, 12, and 16 weeks or until resolutionb,d
 

Abbreviations: CTCAE = Common Terminology Criteria for Adverse Events; ECHO = echocardiogram; LLN = lower limit of normal; LVEF = left ventricular ejection fraction;

a. If ECHO does not show LVEF recovery after 2 weeks, repeat ECHO 2 weeks later.

b. If recurrent episodes of LVEF reduction occur in subjects receiving dabrafenib monotherapy, consult Global Clinical Lead.

c. Symptoms may include: dyspnea, orthopnea, and other signs and symptoms of pulmonary congestion and edema.

d. Once LVEF recovers, including resolution of symptoms, restart of dabrafenib monotherapy only can be considered in consultation with Novartis Global Clinical Lead.

### 5.8.3.2. Hypertension

Increases in blood pressure have been observed in subjects receiving trametinib.

Recommendations for blood pressure monitoring and management are provided in Section [5.8.3.2.1](#) and Section [5.8.3.2.2](#).

**5.8.3.2.1. Monitoring of Hypertension**

All blood pressure assessments should be performed under the following optimal conditions:

- The subject has been seated with back support, ensuring that legs are uncrossed and flat on the floor.
- The subject is relaxed comfortably for at least 5 minutes.
- Restrictive clothing has been removed from the cuff area and the right cuff size has been selected.
- The subject's arm is supported so that the middle of the cuff is at heart level.
- The subject remains quiet during the measurement.

In subjects with an initial blood pressure reading within the hypertensive range, a second reading should be taken at least 1 minute later, with the 2 readings averaged to obtain a final blood pressure measurement. The averaged value should be recorded in the eCRF.

Persistent hypertension is defined as an increase of systolic blood pressure (SBP) > 140 mm Hg and/or diastolic blood pressure (DBP) > 90 mm Hg in three consecutive visits with blood pressure assessments from two readings collected as described above. Visits to monitor increased blood pressure can be scheduled independently from the per- protocol visits outlined in the Time and Events ([Table 19](#)). Ideally, subsequent blood pressure assessments should be performed within one week.

Asymptomatic hypertension is defined as an increase of SBP >140 mm Hg and/or DBP >90 mm Hg in the absence of headache, light-headedness, vertigo, tinnitus, episodes of fainting or other symptoms indicative of hypertension.

**5.8.3.2.2. Management of Hypertension**

For subjects experiencing an increase in systolic and/or diastolic blood pressure that is persistent and may be associated with the study treatment, recommendations for the clinical management of hypertension are described below in [Table 7](#):

**Table 7 Management and Dose Modification Guidelines for Hypertension**

Hypertension	Action and Dose Modification
(Scenario A) 
 
• Asymptomatic and persistenta SBP of >140 and <160 mmHg, or DBP ≥90 and <100 mmHg,
 
 or 
 
• Clinically significant increase in DBP of 20 mmHg (but still below 100 mmHg).
 
	
 
• Continue study treatment at the current dose
 
• Adjust current or initiate new antihypertensive medication
 
• Titrate antihypertensive medication(s) during the next 2 weeks as indicated to achieve well-controlledb BP
 
• If BP is not well controlled within 2 weeks, consider referral to a specialist and go to scenario (B).
 

(Scenario B) 
 
• Asymptomatic SBP ≥160 mmHg, or DBP ≥100 mmHg,
 
 or 
 
• Failure to achieve well-controlled BP within 2 weeks in Scenario A
 
	
 
• Interrupt study treatment if clinically indicated.
 
• Adjust current or initiate new antihypertensive medication(s).
 
• Titrate antihypertensive medication(s) during the next 2 weeks as indicated to achieve well-controlled BP
 
• Once BP is well controlledb, restart study treatment reduced by one dose level
 

or 
 
• Symptomaticc hypertension
 
• Persistent SBP ≥160 mmHg, or DBP ≥100 mmHg, despite antihypertensive medication and dose reduction of study treatment
 
	
 
• Interrupt study treatment
 
• Adjust current or initiate new antihypertensive medication(s)
 
• Titrate antihypertensive medication during the next 2 weeks as indicated to achieve well-controlled BP
 
• Referral to a specialist for further evaluation and follow-up is recommended
 
• Once BP is well controlled, restart study treatment reduced by one dose level
 

Refractory hypertension unresponsive to above interventions or hypertensive crisis.	
 
• Permanently discontinue study treatment
 
• Continue follow-up per protocol.
 

BP = blood pressure; DBP = diastolic blood pressure; mmHg = millimetres mercury; SBP = systolic blood pressure;

a. Hypertension detected in two separate readings during up to three consecutive visits

b. Well-controlled blood pressure defined as SBP ≤140 mm Hg and DBP ≤90 mm Hg in two separate readings during up to three consecutive visits.

c. Symptomatic hypertension defined as hypertension aggravated by symptoms (e.g., headache, light-headedness, vertigo, tinnitus, episodes of fainting) that resolve after the blood pressure is controlled within the normal range

### 5.8.3.3. Guidelines for Prolonged QTc

Guidelines for dose modification and stopping criteria due to QTc-prolongation are provided in [Table 8](#)

Table 8 Withholding and Stopping Criteria for QTcB-Prolongation

QTc-Prolongation a	Action and Dose Modification

 
• QTcB <math>\geq</math>501 msec
 
	
 
• Interrupt all study treatments until QTcB prolongation resolves to grade 1 or baseline
 
• Test serum potassium, calcium, phosphorus and magnesium. If abnormal correct per routine clinical practice to within normal limits.
 
• Review concomitant medication usage for agents that prolong QTc.
 
• If event resolves, restart study treatment at lower dose level or current dose levelb
 
• If event does not resolve, permanently discontinue study treatments. Consider evaluation with cardiologist.
 
• If event recurs, permanently discontinue study treatments. Consider evaluation with cardiologist.
 

Abbreviations: msec = milliseconds; QTcB = QT interval on electrocardiogram corrected using the Bazett's formula.

- Based on average QTc value of triplicate ECGs. For example, if an ECG demonstrates a prolonged QT interval, obtain two or more ECGs over a brief period, and then use the averaged QTc values of the three ECGs to determine if study treatments should be interrupted or discontinued.
- If the QTc prolongation resolves to grade 1 or baseline, the subject may resume study treatment if the investigator and Novartis Global Clinical Lead agree that the subject will benefit from further treatment.

French Only See [Appendix 9](#), for Valvular Toxicity criteria

### 5.8.4. Guidelines for Skin-related Adverse Events on the dabrafenib and trametinib combination treatment arm

Cutaneous adverse events have been observed in subjects receiving dabrafenib, trametinib or both therapies in combination (see the Investigator Brochures for more information); [GlaxoSmithKline Document Number [HM2009/00151/02](#) 2011; GlaxoSmithKline Document Number [CM2010/00010/02](#) 2011 and GlaxoSmithKline Document Number [2011N126811\\_00](#).2012]. Recommendations for supportive care and guidelines for dose modifications are provided (Section [5.8.4.1](#), Section [5.8.4.2](#) and Section [5.8.4.3](#)). The institutional standards for the management of skin-related AEs can differ from these guidelines. In this case, best clinical judgment should be applied and a consultation with the Novartis Global Clinical Lead may be required. In addition, the Sponsor may require biopsies of any new skin lesions especially those suspicious of cuSCC and keratoacanthomas (KA) for further study.

#### 5.8.4.1. Rash

Rash is a frequent AE observed in subjects receiving trametinib, dabrafenib, or the combination of both therapies. Guidelines for rash management are based on experience with other MEK inhibitors and EGFR inhibitors [[Balagula](#), 2010; [Lacouture](#), 2011].

**Table 9 Guidelines for Supportive Care of Rash**

Type of Care	Action
Prevention/Prophylaxis Start from Day 1 a	
 
• Avoid unnecessary exposure to sunlight
 
• Apply broad-spectrum sunscreen (containing titanium dioxide or zinc oxide) with a skin protection factor (SPF) <math>\geq 15</math> at least twice daily.
 
• Use thick, alcohol-free emollient cream (e.g., glycerine and cetomacrogol cream) on dry areas of the body at least twice
 

Prevention/Prophylaxis Start from Day 29 and implement for a total of 6 weeks	
 
• Topical steroids and antibiotics should be applied at least twice daily starting on Day 29 of study treatment, to body areas such as face, chest, and upper back.               
 
○ Use mild-strength topical steroid (hydrocortisone 1% cream)
 
or
 
○ Topical antibiotic (e.g., clindamycin) or oral antibiotics (e.g., doxycycline 100 mg BID, minocycline 100 mg BID)
 
 
 

Symptomatic Care	
 
• Pruritic lesions: cool compresses and oral antihistamine therapies
 
• Fissuring lesions: Monsel's solution, silver nitrate, or zinc oxide cream
 
• Desquamation: thick emollients and mild soap
 
• Paronychia: antiseptic bath, local potent corticosteroids in addition to oral antibiotics; if no improvement, consult dermatologist or surgeon
 
• Infected lesions: appropriate bacterial/fungal culture-driven systemic or topical antibiotics
 

BID = twice daily; SPF = skin protection factor

- a. Subjects who develop rash/skin toxicities should be seen by a qualified physician and should receive evaluation for symptomatic/supportive care management

Guidelines for management and dose adjustment for rash considered to be related to study treatment are provided in [Table 10](#)

**Table 10 Management and Dose Modification Guidelines for Rash**

CTCAE	Adverse Event Management	Action and Dose Modification
Grade 1	
 
Initiate prophylactic and symptomatic treatment measures
 
Use moderate strength topical steroida
 
Reassess after 2 weeks
 
	
 
Continue study treatment
 
If rash does not recover to baseline within 2 weeks despite best supportive care, reduce study treatment by one dose levelb
 

Grade 2	
 
Initiate prophylactic and symptomatic treatment measures
 
Use moderate strength topical steroida
 
Reassess after 2 weeks
 
	
 
Reduce study treatment by one dose level 
 
If rash recovers to <math>\leq</math>grade 1 within 2 weeks, increase dose to previous dose level
 
If norecovery to <math>\leq</math>grade 1 within 2 weeks, interrupt study treatment until recovery to <math>\leq</math>grade 1
 
 
 
Restart study treatment at reduced dose levelb
 

Grade<math>\geq</math>3	
 
Use moderate strength topical steroidsa PLUS oral methyl-prednisolone dose pack
 
Consult dermatologist
 
	
 
Interrupt study treatment until rash recovers to grade <math>\leq</math>1
 
Restartb with study treatment reduced by one dose levelc
 
If no recovery to grade <math>\leq</math>2 within 4 weeks, permanently discontinue study treatment
 

CTCAE = Common Terminology Criteria for Adverse Events

a. Moderate-strength topical steroids: hydrocortisone 2.5% cream or fluticasone propionate 0.5% cream.

b. Approval of Novartis Global Clinical Lead is required to restart study treatment after >21 days of interruption.

c. Escalation of study treatment to previous dose level may be considered if no rash is evident 4 weeks after restarting study treatment

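### Protocol Table 10 (rash) conflicts with Section 5.8.1 on when the dose may go back up, and its own rows give opposite directions for a grade 1 rash at 2 weeks

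*Protocol*

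**What the plan says.** **Section 5.8.1 (text under Table 4).** This paragraph covers any adverse event and makes no exception for rash. Once the event is at grade 1 or baseline at the reduced dose, and "no additional toxicities are seen after 4 weeks of study treatment at the reduced dose, the dose may be increased" to the previous level. A note in the same section requires sponsor approval to restart after an interruption of 21 days or more.

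**Table 10, Grade 1 row.** Treatment continues, but "If rash does not recover to baseline within 2 weeks despite best supportive care", study treatment is reduced by one level.

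**Table 10, Grade 2 row.** Study treatment is reduced by one level at once. On recovery to grade 1 or lower the row says "grade 1 within 2 weeks, increase dose to previous dose level". Without that recovery, treatment is interrupted.

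**Table 10, Grade 3 or higher row.** Treatment is interrupted until the rash is at grade 1 or lower, then restarted one level down. If the rash has not recovered to grade 2 or lower "within 4 weeks, permanently discontinue study treatment". Footnote c adds: "Escalation of study treatment to previous dose level may be considered if no rash is evident 4 weeks after restarting study treatment".

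**Approval to restart.** Table 10 footnote b: "Approval of Novartis Global Clinical Lead is required to restart study treatment after >21 days of interruption". Table 5 footnote b: "Approval from the Novartis Global Clinical Lead is required to restart study treatment after ≥21 days".

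**The concern.** A site treating a grade 2 rash that improves on the reduced dose finds two instructions with different timing and no statement of which prevails. A site looking at a grade 1 rash after 2 weeks finds that Table 10 directs the dose down in one row and up in the next. Both questions arise in routine use, since Section 5.8.4.1 itself describes rash as a frequent event on these drugs.

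What is at stake is dosing and its documentation. Dose level depends on which line is followed. A subject can be off both drugs with no rule that ends the interruption. Permanent discontinuation cannot be reversed, because Section 4.2.1 does not allow retreatment afterwards. On the reporting side, SAP Sections 12.1, 12.3 and 12.5 summarise average daily dose, reductions, interruptions, and the action taken for skin toxicities. Those summaries are harder to interpret if the rules behind the actions are ambiguous.

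**Working it through.** The plan states no figure on this point that could be reproduced. The check sets the rules side by side, condition by condition.

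**1. Time to re-escalation after a grade 2 rash**
- Table 10, Grade 2 row: recovery within 2 weeks, so the increase is triggered by day 14 at the latest. The wording is an instruction.
- Section 5.8.1: 4 weeks at the reduced dose, so not before day 28. The wording is a permission.
- Difference: 28 − 14 = at least 14 days for the same rash.
- Scale of those 14 days at the first reduction level in Table 4 (dabrafenib 150 to 100 mg twice daily, trametinib 2 to 1.5 mg once daily): dabrafenib 14 × 2 × (150 − 100) = 1,400 mg out of 14 × 2 × 150 = 4,200 mg, or 33%; trametinib 14 × (2 − 1.5) = 7 mg out of 14 × 2 = 28 mg, or 25%.
- Comparison with other event-specific rules: wherever the tables for pyrexia (Table 11), diarrhea (Table 12), renal insufficiency (Table 13) and pneumonitis (Table 16) give an interval for going back up, it is 4 weeks. So is footnote c of Table 10, for grade 3 or higher. The Grade 2 rash row is the only one at 2 weeks, and nothing says whether that is a deliberate exception.

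**2. A rash at grade 1 after 2 weeks, within Table 10**
- Began at grade 1 and is not back to baseline: reduce one level.
- Began at grade 2, was reduced, and has improved only to grade 1: increase one level.
- The observed grade is the same and the directions are opposite. After the increase, a rash that stays at grade 1 meets the Grade 1 row, which calls for a reduction after a further 2 weeks.

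**3. Grade 3 or higher row, by grade at week 4 of the interruption**
- Grade 0 or 1: restart.
- Grade 2: neither the restart condition nor the discontinuation condition is met. Treatment stays interrupted, with no time limit.
- Grade 3 or 4: discontinue.
- No grade receives two conflicting actions, so this is a gap. It arises because the row uses grade 1 as the threshold for restart and grade 2 as the threshold for discontinuation. The Grade 2 and Grade 3 rows of Table 16 use a single threshold for both decisions.

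**4. Sponsor approval to restart**
- 20 days of interruption: not required under either wording.
- 21 days: required by Section 5.8.1 and Table 5, not by Table 10.
- 22 days: required under both.
- The rules part on exactly one day.

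**The case against.** The best defence is structural. Section 5.8 separates general from event-specific guidelines, Table 3 sends rash to Section 5.8.4.1, and Section 5.8.2 confines Table 5 to events without a specific guideline. On that reading Table 10 simply governs rash. Section 5.8.1 is also permissive: it says when an increase may be made and does not expressly forbid a shorter interval. This has force, but the limit in Section 5.8.2 is written for Table 5 and not for Section 5.8.1, and no sentence gives Table 10 precedence over the latter. Nor can precedence settle point 2 or point 3, which lie inside Table 10.

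On point 2, the two rows describe different courses: one rash persisting despite supportive care, the other improving on a lower dose. That is fair. A reader might infer endless cycling of the dose. Table 10 alone does not support this, because the Grade 1 row contains no instruction to increase. What remains is one increase that may be followed by another reduction.

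On point 3, a reader might call the row contradictory. It is not. The instruction to stay interrupted still applies at grade 2, a restart after 4 weeks would need sponsor approval under either day limit, and Section 4.2.1 leaves discontinuation open to the investigator. The missing end rule is what stands.

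Finally, Section 5.8.4 accepts that institutional standards for skin events may differ from the guidelines and calls for clinical judgment in that case. Some variation between sites is therefore already allowed. That does not tell a site what the guideline is when its own lines disagree.

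**Conclusion.** The inconsistency is real and worth correcting. Two parts carry the point: the conflict of at least 14 days between Section 5.8.1 and the Grade 2 row, with no stated precedence, and the opposite directions in Table 10 for a rash at grade 1 after 2 weeks. The week-4 grade 2 state is a gap. The approval limit is a minor mismatch, confined to an interruption of exactly 21 days.

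Three stronger conclusions are tempting but unsupported:
- **That the same rash is in fact dosed differently across sites.** The wording makes this possible; nothing in the documents demonstrates it, and Section 5.8.4 already allows some variation.
- **A count of affected subjects.** A reader might apply the 14% rate of grade 2 or higher skin toxicity from the earlier combination study (Section 1.1.3.2) to the planned 120. That rate covers all skin toxicity, not rash alone, and pools four dose levels. The amendment rationale also reports only 9 patients still on treatment, so an amended rule would reach few.
- **An effect on the primary analysis.** None is shown or claimed. The SAP lists no display of re-escalations, so any trace would be indirect, for example through average daily dose.

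The milligram figures in the working assume a subject at the first reduction level who takes every dose. They show scale only.

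**What to change.** The sponsor's clinical team should reconcile Section 5.8.1, Table 5 and Table 10:
- State whether Table 10 takes precedence over Section 5.8.1 for rash, and write any exception into Section 5.8.1.
- Make the Grade 1 and Grade 2 rows consistent for a rash at grade 1 after 2 weeks.
- Assign an instruction to a rash at grade 2 at week 4 of an interruption for grade 3 or higher.
- Use one day limit for sponsor approval throughout.

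The choice of intervals, grades and limits is clinical, and none is proposed here. The cost is wording in one table, one paragraph and the approval notes, made in a protocol amendment. No analysis or sample size changes.
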